18.4.1.3 Overall Response Rate Scenarios

Due to the ‘borrowing’ nature of the model, the design is evaluated across a variety of scenarios for the distribution of true ORRs across the histologic cohorts. These are shown in Table 33.

The “Alternative ” scenario assumes all histologies are responsive at the defined clinically meaningful RR levels. The “Null” case assumes all histologies are non- responsive at the historical control RRs. The “All Moderate” scenario assumes all histologies show moderate RR levels inbetween the historical control and clinically meaningful RR levels. The “Mixed (0.1-0.5)” assumes a range of response rates across the nine histologies. The other three scenarios consider various situations where histologies are either responsive (at the clinically meaningful RR level) or not (at the historical control RR level).

Table 33 Simulation Scenarios: Various Assumptions for the True ORR for each Histology

Scenario	Histology								
	1	2	3	4	5	6	7	8	9
Alternative	50%	50%	60%	50%	50%	50%	50%	60%	75%
Null	10%	10%	15%	10%	10%	10%	10%	15%	25%
All Moderate	30%	30%	40%	30%	30%	30%	30%	40%	50%
Mixed	50%	10%	30%	40%	10%	20%	30%	45%	75%
5 Greats: Mixed	50%	10%	60%	10%	50%	10%	10%	60%	75%
5 Greats: Low	10%	10%	15%	10%	50%	50%	50%	60%	75%
2 Greats	10%	50%	15%	10%	50%	10%	10%	15%	25%

Abbreviations: ORR = overall response rate

NOTE: Color indicates responsiveness of the true ORR for each histology. Red indicates non-responsive and is equal to the assumed historical control rate, green indicates responsive and is equal to the clinically meaningful ORR, and blue indicates moderate responsiveness and is in-between the historical control rate and clinically meaningful ORR.

18.4.1.4 Output from Simulated Trials

For each scenario specified in Table 33, overall descriptive measures are reported for each histology and sample sizes specified in Case 1 and include:

- Proportion of studies that declare the histology efficacious at the final analysis
- Proportion of studies that halt enrollment to each histology early for futility
- Proportion of studies that halt enrollment to each histology early for efficacy
- For each possible combination of sample size and observed number of responses, the proportion and number of times the model declares such data efficacious at the final analysis (by scenario, combining across histologic cohorts)

In-depth information is also provided for a small number of simulated example trials. These illustrate the flow and outcome of possible trials based on the pre-specified statistical decision rules.

18.4.2 Operating Characteristics

18.4.2.1 Power and Type I Error Rate

[figure not shown]
Power and type I error rate are examined across scenarios for the distribution of assumed true ORRs for each histology. The power is the probability of declaring efficacy within a histology when the true underlying ORR is greater than its corresponding historical control. Type 1 error rate is the probability of declaring efficacy within a histology when the true underlying response rate is equal to the historical control. [Figure 1](#) illustrates the proportion of trials that declare each histology efficacious at the final analysis across simulation scenarios. Supporting tables for the simulation results are provided in [Appendix 7](#).

The power and type I error rate are dependent upon the sample sizes and response rates across the distribution of histologies. When the treatment effects are the same across all histologies (either all responsive or all non-responsive), estimation efficiencies, due to borrowing, result in very good operating characteristics, even in histologies with very low sample sizes. Under sample size Case 1, the type I error rate is controlled to ≤ 0.04 across all histologies (All Null scenario). The design maintains power 93% to 98% for the higher enrolling cohorts, and 84%

to 90% for the smallest enrolling 5 cohorts (All Great scenario). Also, the design exhibits reasonable power to detect a moderate level of activity (All moderate scenarios).

When the treatment effects vary across histologies, the amount of appropriate borrowing also varies, impacting the operating characteristics. The ‘2 Greats: Mixed’ investigates design performance where most histologies are not responsive. In this situation, the type I error rate is controlled to ≤ 0.06 and the power is 82% for the higher enrolling cohort and 55% for the low enrolling cohort. The ‘5 Greats: Mixed’, ‘5 Greats: Low’ and ‘Mixed’ scenarios investigate the design performance in situations where roughly half the histologies are responsive. The type I error rate ranges from 0.09 to 0.14 while the power ranges from 93% to 96% for the higher enrolling cohorts and ranges from 67% to 84% for the lower enrolling cohorts. Generally, improvement in the overall distribution of treatment effects tends to coincide with slight increases in type I error rate and moderate increases in power.

Figure 1 Proportion of Studies that Declare each Histology Efficacious at the Final Analysis under Sample Size Case 1

18.4.2.2 Probability that the Model Declares Success Across Different Sample Sizes and Numbers of Observed Responses

No pre-determined number of responses or response rate will necessarily dictate model success or model failure. In addition to a particular histology response data, their corresponding historical control response rate and the overall distribution of treatment effects across the histologies impacts the model decision in that particular histology. To further understand the likelihood of model success, for each possible combination of sample size (≤ 15) and number of observed responses, the proportion of times the model declares such data efficacious at the final analysis is assessed by scenario but combining across histologic cohorts with the same historical control response rate. Hence, the likelihood of declaring success is explored for histologies with historical control response rates of 0.10 (histologies 1, 2, 4, 5, 6, and 7), 0.15 (histologies 3 and 8), and 0.25 (histology 9). Actual histologies, their simulation indexing number, and the appropriate historical control response rates are in [Table 29](#) in Section 18.4.1.3.

Figure 1 illustrate the proportion of trials that declare success across all possible combinations of sample sizes and number of observed responses and for each historical control response rate. Figure 2 illustrates a subset of this data, more clearly describing the probability of declaring success when 1, 2, 3, or 4 responses are observed.

Supporting tables for these simulation results are provided in Appendix 7. Some variability is expected in these estimates due to low sample sizes in some of these observed data combinations.

Should statistical success be met while only a moderate response rate observed, it will be critical that the entirety of the data, including secondary efficacy endpoints, support a meaningful high level of activity to demonstrate evidence of a very large treatment effect. Based on the decision criteria, data from at least two subjects must be available to declare success. Hence, if data is only available for 1 subject, the success criteria will not be met, regardless of that 1 subject’s response status. When the observed ORR is $\leq 10\%$, success is never declared for any histology across all seven scenarios. Hence, if zero responses are observed, a histology will never meet the success criteria. And, at least two responses are needed if response data is available for more than 10 subjects within a particular histology.

When one response is observed within a histology, there is positive probability of meeting success only in mixed situations when the sample size is small (roughly ≤ 5). When 2, 3 or 4 responses are observed, there is increasing probability of meeting success, but this is largely dependent upon the overall distribution of treatment effects as well as the final sample size. Also, the probability of declaring success for a particular dataset is higher for histologies with lower historical control response rates. Five responses are almost always sufficient to meet statistical success regardless of the sample size, scenario, and historical control response rate. Further details for all situations can be visually explored in Figure 3.

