18.2 Sample Size Considerations

18.2.1 Sample Size Assumptions

Each cohort of BRAF V600E mutation-positive tumor type of a given histology will enroll a maximum of 25 subjects **in the primary analysis cohort as defined in Section 5.1**. If all histologies enroll the maximum of 25 subjects, this will result in no more than 225 subjects in the primary analysis cohort.

Enrollment into specific histology cohorts may be halted early based on results from interim analyses incorporating emerging response data. Response data from a minimum of 5 subjects will be required in a histologic cohort before it may discontinue enrollment for futility and response data from a minimum of 10 subjects will be required before discontinuing a histologic cohort for efficacy. **If a cohort closes early for efficacy at an interim analysis, a histology specific expansion cohort (see Section 5.2) may be opened to allow additional enrollment.** At the final analysis and after the study has been closed, a minimum of 2 subjects will be required in a histologic cohort in order to meet statistical success at the final analysis. See Section [18.3.2](#) for more details.

Simulation studies were conducted to evaluate the performance of the design under various assumptions for the distribution of true ORRs across the histologic cohorts and accounting for the anticipated small sample sizes (refer to Section [18.4.1.2](#)). Operating characteristics including power, type I error, estimation of the ORR, and the probability of halting enrollment at interim analyses were assessed.

When the treatment effects are similar across all histologies, the design maintains power 84% to 98% and type I error rate ≤ 0.04 . Estimation efficiencies due to borrowing result in very good operating characteristics in these situations, even in histologies with very low sample sizes.

In mixed scenarios where some histologies show large treatment effects and others do not, the type I error can range from 0.03 to 0.14 while the power ranges from 55%- 96%. This variation is hugely dependent upon the expected sample sizes of the individual histologies as well as the overall distribution of treatment effects across the histologies.

Full presentation and discussion of the simulation parameters and corresponding simulation results are in Section [18.4](#).

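### The power ranges in Sections 18.2.1, 18.4.2.1 and 18.4.2.3 hold only for cohorts at the clinically meaningful ORR, although power is defined for any true ORR above the historical control

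*Protocol*

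**What the plan says.** Section 18.4.2.1 gives the definition: "The power is the probability of declaring efficacy within a histology when the true underlying ORR is greater than its corresponding historical control". It does not require the true ORR to reach the clinically meaningful rate in Table 29.

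The same section groups '5 Greats: Mixed', '5 Greats: Low' and 'Mixed', and reports for Case 1 that "power ranges from 93% to 96% for the higher enrolling cohorts and ranges from 67% to 84% for the lower enrolling cohorts". According to Section 18.4.1.3, 'Mixed' "assumes a range of response rates across the nine histologies".

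For equal effects, Section 18.4.2.1 gives 93-98% for the higher enrolling cohorts and 84-90% for the five smallest, and labels this the All Great scenario. Section 18.2.1 merges the two without the label: "When the treatment effects are similar across all histologies, the design maintains power 84% to 98% and type I error rate". For scenarios with a mixture of large and absent effects it gives 55-96%.

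Section 18.4.2.3 gives 94-98% (Case 2) and 92-98% (Case 3) for cohorts with more than 10 subjects. Sections 18.4.2.1 and 18.4.2.3 both describe power at a moderate level of activity only as reasonable, without a number in the text.

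**The concern.** Under the protocol's definition, a cohort whose true rate is double or triple its control counts towards power. Table 33 contains many such cohorts: all nine in 'All Moderate' and five in 'Mixed'. If the printed ranges leave them out without saying so, the protocol states a power that the design does not have.

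This matters when a cohort misses the 92% rule. The Appendix 8 examples label every miss as futility. A reader who has been told that power is 84-98% for similar effects, or 67-96% in 'Mixed', would take a miss as strong evidence of inactivity. For a cohort with a moderate effect, a miss can be about as likely as a success, or more likely.

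**Working it through.** **Inputs.** Case 1 sizes and control rates come from Table 32, and true ORRs from Table 33. The decision rules come from Sections 18.3.2 and 18.3.3.2, the interim timing and 8-week response lag from Section 18.4.1, and the model from Appendix 6.

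**Step 1: which 'Mixed' cohorts are intermediate.** HCL (50%) and NSGCT/NGGCT (75%) are at the clinically meaningful ORR. BTC and WHO Grade 3/4 glioma (10%) are at control. The other five lie between.

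**Step 2: bounds that need no model, at the projected n.** Section 18.4.2.2 says of an observed ORR of 10% or less that "success is never declared for any histology across all seven scenarios".
- ATC, n = 10, p = 0.30: at least 2 responses are needed, so power ≤ 1 − 0.7^10 − 10(0.3)(0.7^9) = 85.1%. The stated range starts at 93%.
- WHO Grade 1/2 glioma, n = 5, p = 0.20: if a single response were always enough, power = 1 − 0.8^5 = 67.2%. If two were needed, 1 − 0.8^5 − 5(0.2)(0.8^4) = 26.3%.
- GIST, n = 5, p = 0.30: if two responses were needed, 1 − 0.7^5 − 5(0.3)(0.7^4) = 47.2%.
- 'All Moderate', n = 5, p = 0.30: power ≤ 1 − 0.7^5 = 83.2%, below the 84% in Section 18.2.1.

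**Step 3: reproduce the protocol's figures.** The Appendix 6 model was coded with exact summation over all groupings of the nine histologies. It matches all 54 final decisions in the Appendix 8 examples, and the largest difference in posterior probability is 0.026. Whole trials were then simulated for Case 1 with Poisson accrual:
- Alternative: 94-98% (histologies 1-4) and 84-91% (5-9); stated 93-98% and 84-90%.
- Null: type I error at most 0.04; stated at most 0.04.
- Cohorts at the clinically meaningful ORR in the two '5 Greats' scenarios and 'Mixed': 95-97% and 68-82%; stated 93-96% and 67-84%.
- '2 Greats': 85% and 56%; stated 82% and 55%.

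The printed ranges are therefore closely reproduced when only cohorts at the clinically meaningful ORR are counted.

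**Step 4: intermediate cohorts in 'Mixed'** (4000 Poisson trials, Monte Carlo SE about 0.8 points; 1000 fixed-n trials, SE about 1.6 points).

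| Cohort | n | True ORR / control | Poisson | Fixed n |
|---|---|---|---|---|
| ATC | 10 | 30% / 15% | 47% | 50% |
| ASI | 8 | 40% / 10% | 76% | 80% |
| WHO Grade 1/2 glioma | 5 | 20% / 10% | 28% | 25% |
| GIST | 5 | 30% / 10% | 45% | 47% |
| MM | 5 | 45% / 15% | 59% | 70% |

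For 'All Moderate', power is 51-76% with Poisson accrual and 48-80% with fixed n.

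**Step 5: the sponsor's own table.** In Appendix 7, scenario Mixed1, histology 2 (n = 16, 30% against 10%) has 0.74 in Case 2 and 0.77 in Case 3. Histology 5 (n = 16, 40% against 10%) has 0.90 in both. Section 18.4.2.3 states 94-98% and 92-98% for cohorts of this size. The simulation gives 0.79 and 0.91 for Case 2. Only these two entries are used, because other entries in that row do not fit Table 34: histology 8, set at its 15% control rate, is listed at 0.48.

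**The case against.** The strongest reply is that the ranges were meant for responsive cohorts. Section 18.1 says that the study is powered for a high, clinically meaningful rate, and the note to Table 33 reserves the word responsive for that rate. This explains the figures but does not repair the text. Section 18.4.2.1 says that roughly half the histologies are responsive in the three scenarios. In 'Mixed', two of nine are at the clinically meaningful ORR and seven of nine are above control, and neither is about half. The definition of power in the same section also covers all seven.

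Several stronger readings are tempting, and the documents do not support them:
- **That the simulations are wrong.** The ranges reproduce for cohorts at the clinically meaningful ORR.
- **That Section 18.2.1 promises at least 67% in mixed scenarios.** It gives 55-96%, introduces the range with "In mixed scenarios where some histologies show large treatment effects and others do not", and stresses its dependence on sample size.
- **That 84-98% is unlabelled throughout.** Section 18.4.2.1 attaches the All Great label; only the summary in 18.2.1 drops it.
- **That all five intermediate cohorts must fall short.** MM reaches 70% with fixed n, and ASI is inside 67-84% if n = 8 counts as lower enrolling. The protocol does not define the split at that point.
- **That moderate-effect power is unreported.** Section 18.4.2.1 says that Figure 1 shows results for each histology across the scenarios. The figure is not visible in the copy reviewed, so it may contain these values.
- **That a miss says nothing about a moderate effect.** With power 0.49 and type I error 0.12, a miss has likelihood ratio (1 − 0.49)/(1 − 0.12) = 0.58 for moderate against null. That is weak evidence against a moderate effect, but not none.

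It is also fair that the bounds in Step 2 assume exactly the projected n. If ATC enrolment is Poisson with mean 10, the ATC bound rises to about 91%, still under 93%.

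**Conclusion.** The stated power is wrong as written, in scope rather than in calculation. Under the definition in Section 18.4.2.1, ATC, WHO Grade 1/2 glioma and GIST in 'Mixed' have power of about 47-50%, 25-28% and 45-47%. These values are below both the Section 18.4.2.1 ranges and the 55% floor in 18.2.1. MM (about 59-70%) and ASI (about 75-80%) are below or near the ranges, depending on accrual and on how higher enrolling is read. On its wording, Section 18.2.1 also covers 'All Moderate', where power is about 48-80% rather than 84-98%. Section 18.4.2.3 conflicts with Appendix 7 for two cohorts of 16.

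The simulated values rest on four assumptions: η in Appendix 6 is the historical control, the 3 in N(0,3) is a variance, accrual is Poisson or fixed, and Case 1 cohorts are capped at 15. The ATC and 'All Moderate' bounds at the projected n, and the Appendix 7 comparison, need none of these. No decision rule, estimate or planned analysis is affected.

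**What to change.** In Sections 18.2.1, 18.4.2.1 and 18.4.2.3, state that the power ranges apply only to cohorts whose true ORR equals the clinically meaningful ORR in Table 29. In 18.4.2.1 and 18.4.2.3, replace the unquantified statement about moderate activity with the sponsor's own simulated power for the intermediate cohorts in 'All Moderate', 'Mixed' and Mixed1, after checking the Mixed1 rows of Appendix 7 against Table 34. The figures given here are a check and should not be inserted in place of the sponsor's output. The SAP needs no change.

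The cost is wording plus output that should already exist. The stated power becomes less favourable for moderate effects.

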18.4.2.3 Probability that the Model Declares Success Across Different Sample Sizes

To evaluate the model performance for various sample sizes, simulations are also performed under the following four scenarios for sample sizes specified in Case 2, 3, and 4 with the maximum sample size for a given histology can be as high as 25.

Table 34 Simulation Scenarios for Enrollment Sensitivity: Various Assumptions for the True ORR for Each Histology

Scenario	Histology								
	1	2	3	4	5	6	7	8	9
Mixed1	20%	30%	60%	30%	40%	40%	10%	15%	75%
5 Greats: Mixed1	10%	50%	60%	50%	10%	50%	10%	15%	75%
4 Greats: Low	10%	10%	15%	50%	10%	50%	50%	15%	75%
2 Greats: Mixed1	10%	10%	60%	10%	10%	10%	50%	15%	25%

When the sample size for some histology increases from 15 to 25, the largest type I error increases from 0.14 to 0.18. Under sample size Case 2, the type I error rate is ranges from 0.04-0.17; the design maintains power 94% to 98% for the higher enrolling cohorts (>10 subjects enrolled per cohort), and 61% to 87% for the smallest enrolling three cohorts (5 subjects enrolled per cohort). Under sample size Case 3, the type I error rate is ranged from 0.04 to 0.18; the power is ranged from 92% to 98% for high enrolling cohorts (>10 subjects enrolled per cohort) and ranged from 62% to 86% for low enrolling cohorts (5-8 subjects

enrolled per cohort). Under sample size case 4, the type I error ranges from 0.02 to 0.16; the power ranges from 93% to 96% for high enrolling cohorts (>10 subjects enrolled per cohort), 59% to 71% for low enrolling cohorts (5-8 subjects enrolled per cohort) and 26% to 44% for ultra low enrolling cohorts (2 subjects enrolled per cohort). [Figure 4](#) illustrates the proportion of trials that declare success across all possible combinations of sample sizes and number of observed responses and for each historical control response rate. Supporting tables for the simulation results are provided in [Appendix 7](#).

Also, the design exhibits reasonable power to detect a moderate level of activity. The type I error rate maintains well under different sample size scenarios and reasonable power are achieved for cohorts which enroll no less than 5 subjects per cohort. The powers for cohorts that have super low enrollment (n=2 or less) can be lower than 50%. Overall the design performance is robust to overenrolling up to 25 subjects for a given histology.

Figure 2 For Each Combination of Sample Size and Observed Number of Responses, the Probability of Model Success at the Final Analysis (by scenario, combined across histologies with the same historical control RR)

[figure not shown]

Figure 3 For All Sample Sizes and When the Number of Observed Responses is 1, 2, 3, or 4, the Probability of Model Success at the Final Analysis (by scenario, combined across histologies with the same historical control RR)

[figure not shown]
[figure not shown]

Figure 4 Proportion of Studies that Declare Each Histology Efficacious at the Final Analysis under Sample Size Case 2, 3 and 4

Stopping Early [Figure 5](#) and [Figure 6](#) illustrate the proportion of trials that halt enrollment early for futility and efficacy across simulation scenarios. Supporting tables for the simulation results are provided in [Appendix 7](#).

Since the study requires at least five subjects in a particular histology prior to stopping early for futility and 10 subjects in a histology prior to stopping early for efficacy, the ability for histologies to stop early is largely dependent upon the projected maximum sample size per histology. The overall distribution of treatment effects across histologies also impacts the likelihood of halting enrollment early.

When the expected 3-year enrollment is greater than 5, non-responsive histologies stop early for futility between 32% and 66% of the time. When the expected 3-year enrollment is five subjects, non-responsive histologies stop early for futility between 8% and 35% of the time. When the expected 3-year enrollment is at least 10, responsive histologies stop early for futility between 41% and 90% of the time. When the expected 3-year enrollment is less than 10, the probability of stopping early for success is very low. Across simulation scenarios, non-responsive histologies generally do not stop early for efficacy while responsive histologies generally do not stop early for futility.

Figure 5 Proportion of Trials that Halt Enrollment Early for Futility for Each Histology

[figure not shown]
[figure not shown]

Figure 6 Proportion of Trials that Halt Enrollment Early for Success for each Histology

